The categorical term of sepsis includes AE preferred terms of bacterial sepsis, Escherichia sepsis, Klebsiella sepsis, neutropenic sepsis, sepsis, sepsis syndrome, septic shock, and Stenotrophomonas sepsis. Twenty-four (29%) subjects experienced sepsis in this study: 18 (25%) subjects were in Part A and 6 (75%) subjects were in Part B in the R/R AML cohort. No sepsis was reported in the 2 subjects enrolled in the R/R HR-MDS cohort in Part B. The rate of sepsis in the Part B R/R AML cohort (75%, 6 of 8 subjects) was higher than the overall rate (25%, 18 of 72 subjects) of sepsis from Part A Dose Escalation of this study, and it was higher than the rate (18%, 2 of 11 subjects) of sepsis among subjects receiving the same dose of CC-90009 on the same schedule in Part A. In Part A, the incidence of sepsis is 15%, 29% and 36% among subjects receiving consecutive daily CC-90009 doses of 2.4 mg and below (n = 13), 3.0 mg (n = 24), and 3.6 mg and above (n = 25), respectively, demonstrating a potential dose-dependent relationship between CC-90009 and the development of sepsis. There was no sepsis reported in cohorts with

CC-90009 dosed at shorter step intervals (ie, when CC-90009 is dosed on cycle Days 1-3 followed by Days 8-10), and this schedule is not being pursued based on a lack of objective responses.

An exploratory analysis of CC-90009 plasma exposures in subjects who developed sepsis showed that exposures were elevated by approximately 1.56-fold compared to subjects who did not develop sepsis. Additionally, subjects who received strong inhibitors of CYP3A4 enzyme (N=20) showed that exposures were elevated by approximately 1.8-fold (median dose-normalized AUC₂₄ = 192 ng.hr/mL) compared to subjects who did not receive strong CYP3A4 inhibitors or received moderate CYP3A4 inhibitors (N = 59, median AUC₂₄ = 106 ng.hr/mL), suggesting a potential drug-drug interaction of CC-90009 with strong inhibitors of CYP3A4.

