pooled in each cohort by dose level for analysis of safety, PK, and PD, which will include between 6 and 40 subjects with up to 20 subjects with R/R AML and up to 20 subjects with R/R HR-MDS in each cohort. The cohorts will enroll subjects in parallel. Up to 6 subjects per cohort will be initially enrolled as a safety run-in. The SRC will assess tolerability of the dose and schedule for these initial subjects that completed at least one cycle of study treatment based on the Part A stopping criteria (Section 7.2.8) and recommend further expansion of one or more cohorts. The expanded cohort(s) will be monitored for the excess toxicities including sepsis utilizing the non-binding Bayesian stopping criterion on a continuous basis (Section 9.9.3). The SRC will continue to review safety and preliminary efficacy data regularly throughout the study and make recommendations about study continuation, cohort continuation, and dose modification, as appropriate.

The study will be conducted in compliance with International Council for Harmonisation (ICH) of Technical Requirements for Pharmaceuticals for Human Use/Good Clinical Practice (GCP) and applicable regulatory requirements.

Figure 1: Study Schema for Dose-Limiting Toxicity Window in Part A (Dose Escalation)

DLT = dose-limiting toxicity.

^a Modified dosing schedules (eg, increasing from 5 to 10 days) may be evaluated in additional cohorts, if necessary, based on the review by the Safety Review Committee of available safety and laboratory data, PK profiles, and PD findings.

[figure not shown]
^b Progressive disease is defined in Section 6.4.

^c In the absence of progressive disease (or relapse) or unacceptable toxicity, subjects may continue treatment with CC-90009 through Cycle 4 if they are deriving benefit, as judged by the Investigator (refer to Section 6.4). Additional cycles of treatment beyond Cycle 4 may be allowed after discussion with the Medical Monitor if the subject is demonstrating clinical benefit (stable disease or PR) and tolerating the study drug without unacceptable toxicity.

^d Additional bone marrow assessment performed at the time of hematologic recovery or Day 42 (refer to Table 4, Table 31, Table 33, or Table 37).

^e Eligible subjects proceed to Cycle 2.

Figure 2: Sample Dose Escalation Schemes for Part A with an NTD of 8.1 mg Example 1

[figure not shown]
Example 2

Escalations proceed by 100% increments with \geq 1 subject cohorts until:

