9.9.3 Stopping Rules Regarding Toxicity in Part B Dose Expansion

During dose expansion phase (Part B), a non-binding Bayesian method will be utilized to monitor excess toxicities defined as the occurrence of AEs during any cycle that would fulfill the DLT criteria specified in Part A or treatment related AEs leading to dose reduction or discontinuation or the occurrence of sepsis. The enrollment in the corresponding expansion cohort will pause to ensure the posterior probability of excess toxicity rate exceeding 25% is not more than 70%, ie, when

Prob (rate of AEs that fulfill the DLT criteria or treatment-related AEs leading to dose reduction or discontinuation or rate of sepsis >0.25|data, a, b) > 0.7.

Where a, b are parameters of Beta distribution. Weakly informative priors, ie, Beta (0.5, 0.5), may be used to calculate the posterior probability. The excess toxicity rate of 25% is established based on clinical inputs with threshold of 70% based on empirical data analysis.

After a minimum of 8 subjects have enrolled and taken at least one cycle of study treatment for a cohort, the posterior distributions of excess toxicity will be calculated on a continuous basis for every subject enrolled (Table 15).

The operating characteristics of the proposed Bayesian safety monitoring plan are detailed in Appendix P.

Number of Subjects	Number of Subjects with AEs fulfilling DLT or other criteria that would prompt potential enrollment pause
8	3
10	4
13	5
17	6
21	7
24	8
28	9
32	10
35	11
39	12

Table 15:Stop Boundaries Based on Stopping Criteria for Each Expansion
Cohort

AE = adverse event; DLT = dose limiting toxicity

Note: Only unique stopping boundaries are presented up to the estimated maximum enrollment of 40 subjects in an expansion cohort.

The SRC will convene regularly (eg, monthly) to review the overall safety/tolerability data and to assess the Bayesian analysis output. Each subject that experiences an AE that meets the above criteria will be reviewed by the SRC, and the overall Bayesian Analysis will be run at that time to guide the SRC on cohort decisions. If the stopping rule is triggered, the SRC will conduct a comprehensive review of available safety, PK, PD, and preliminary efficacy data to make continuation decisions. Decisions to pause enrollment of specific expansion cohort(s) or terminate the study will be determined by the SRC and communicated properly to Investigators, IRBs, and appropriate regulatory authorities.

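### The Part B toxicity rule is defined only for AML and HR-MDS pooled at a dose level, so when the two rates differ its trigger depends on accrual mix and order and can miss an excess confined to one disease

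*Combined protocol and SAP*

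**What the plan says.** - **Pooling.** Section 3.1 has the new 2.4 mg and 3.0 mg Days 1-7 subjects "pooled in each cohort by dose level for analysis of safety, PK, and PD", with "up to 20 subjects with R/R AML and up to 20 subjects with R/R HR-MDS in each cohort". Section 1.3.4 also makes pooling definite. The Protocol Summary only permits it.
- **Rule.** Section 9.9.3 pauses enrolment in an expansion cohort to ensure that the "posterior probability of excess toxicity rate exceeding 25% is not more than 70" percent. On the prior: "Weakly informative priors, ie, Beta (0.5, 0.5), may be used to calculate the posterior probability".
- **Looks.** "After a minimum of 8 subjects have enrolled and taken at least one cycle of study treatment for a cohort", the posterior is "calculated on a continuous basis for every subject enrolled".
- **Boundaries.** Table 15 ("Stop Boundaries Based on Stopping Criteria for Each Expansion" Cohort) and Table 39 (Appendix P) both carry a note setting the maximum at 40 subjects per cohort. That is the two diseases together. Each column of Table 39 assumes a single true rate. No boundary, posterior or operating characteristic is given by disease.
- **Background.** Section 1.2.3.1 reports sepsis in 6 of 8 Part B AML subjects at 3.6 mg Days 1-5, and: "No sepsis was reported in the 2 subjects enrolled in the R/R HR-MDS cohort in Part B".
- **Disease separated elsewhere.** Section 7.3 stratifies Part B enrolment by disease cohort, and the futility rule in Section 9.3 counts AML subjects only.

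**The concern.** The pooled posterior estimates a mixture. If one disease has a rate well above 25% and the other well below, whether the boundary is crossed depends on how many subjects of each disease have entered, and in what order, as well as on toxicity in either disease. Table 39 cannot show this, because it assumes a common rate.

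At stake is the only pre-set criterion for excess toxicity, sepsis included, in the expanded Part B cohorts. A cohort could reach full size with an excess in one disease while the reported posterior stays below 0.70, and that value could reassure the SRC when a recommended dose is chosen for that disease. The safety run-in adds no protection by disease: it takes up to 6 subjects per cohort with no disease split, and it uses the Part A criteria, whose DLT definition (Section 7.2.6) exempts Grade 3 or higher infection.

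**Working it through.** **Inputs from the plan.** Limit 25%, threshold 0.70, prior Beta(0.5, 0.5), first look at n = 8, a look after every subject (all 9.9.3); at most 20 + 20 subjects per dose (3.1).

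**Assumptions not in the plan.** The true rates in each disease, a full 20:20 cohort, and the order of entry.

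**1. Reproduce the plan's figures.** The boundary b(n) is the smallest x with Pr(rate > 0.25) = 1 − BetaCDF(0.25; 0.5 + x, 0.5 + n − x) > 0.70. For example, at n = 8, x = 2 gives 0.529 and x = 3 gives 0.800, so b(8) = 3. All ten Table 15 boundaries match.

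Stopping probabilities come from the exact recursion f(n, x) = f(n−1, x)(1 − p) + f(n−1, x−1)p, removing the mass at x ≥ b(n) from n = 8 onward. All 80 cells of Table 39 match within 0.1 point. Looks only at the tabulated n do not match (51.8% against 62.9% at a rate of 25%, n = 39). Table 39 therefore assumes a look at every subject and one common rate.

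**2. Dilution without assumed rates.** Take a 1:1 mix with every event in one disease, at the look shown. Whether an earlier look had already crossed depends on the order of events.

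| Pooled | Boundary | Pooled posterior | That disease alone | Its posterior | Its boundary |
|---|---|---|---|---|---|
| 4/16 | 5 | 0.520 | 4/8 | 0.941 | 3 |
| 5/20 | 6 | 0.518 | 5/10 | 0.959 | 4 |
| 11/40 | 12 | 0.652 | 11/20 | 0.998 | 6 |

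**3. Probability of a trigger, true AML rate 40%, 20 + 20, random order (simulation).**

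| Assumed HR-MDS rate | Pooled rule | Same rule, AML alone |
|---|---|---|
| 5% | 52% | 92% |
| 10% | 64% | 92% |
| 15% | 74% | 92% |
| 20% | 82% | 92% |
| 25% | 89% | 92% |

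**4. Other AML rates.** With HR-MDS at 10% and alternating entry (exact), AML at 35 / 40 / 45 / 50% gives 53 / 64 / 75 / 84% pooled, against 84 / 92 / 97 / 99% for AML alone.

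**5. Order and mix.** At 40% AML and 10% HR-MDS, the pooled rule triggers in 35% of cohorts if HR-MDS enters first, 64% if entry alternates and 92.5% if AML enters first. With four AML entries to each HR-MDS entry until AML is full, it triggers in 87%.

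**6. Symmetry.** With AML at 10% and HR-MDS at 40%, the pooled rule again triggers in about 64%. Adding an AML-only check leaves that figure at about 64%.

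**7. Cost.** Probability of any trigger when both true rates are equal and below the limit:

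| Common true rate | Pooled only | Plus AML check | Plus both disease checks |
|---|---|---|---|
| 10% | 6.5% | 10.5% | about 14% |
| 15% | 19.5% | 28% | about 37% |
| 20% | 40% | 51% | about 61-62% |

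**The case against.** The strongest case for leaving the rule alone has four parts.

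- **Evidence of a disease difference is thin.** 6/8 against 0/2 gives a two-sided Fisher p of 0.13 and comes from a closed regimen. At the same dose and schedule in Part A, AML sepsis was 2 of 11 (18%). Sections 1.2.3.1 and 1.3.4 link sepsis to exposure, and raised exposure to strong CYP3A4 inhibitors, which fits pooling by dose. This stands. It means equal rates cannot be ruled out, but almost no HR-MDS data support assuming them.
- **The SRC would see it anyway.** The rule is non-binding, and Section 9.9.3 has the SRC review every qualifying case. It closed the 3.6 mg cohorts before this rule was added. This also stands: what can be missed is the formal criterion. Judgement without a pre-set criterion is still the weaker safeguard.
- **The gap depends on assumptions.** No HR-MDS rate has a source in the documents, and the endpoint is composite, so 0/2 for sepsis does not supply one. Near 25% in HR-MDS the gap is about 3 points. If accrual repeats the 8:2 seen so far, it is about 5 points.
- **Extra checks raise more reviews** when neither disease has an excess, as step 7 shows.

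A reader might infer that pooling could hide a repeat of the 75% sepsis rate. It would not. With AML at 75% and HR-MDS at 0 to 10%, the pooled rule triggers in over 99% of cohorts by n = 40. The 3.6 mg data, pooled as 6/10, already exceed the boundary of 4 at n = 10. Nor is the rule especially weak for AML: the dilution is symmetric, and HR-MDS is the less studied disease.

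**Conclusion.** The concern holds as a gap in the formal criterion. The rule and its operating characteristics cover only the pooled cohort with one common rate. An excess of about 35% to 50% in one disease can go unflagged when the other disease's rate is clearly below 25%. At an assumed 40% in AML the loss runs from 40 points (HR-MDS at 5%) to 3 points (HR-MDS at 25%) under random 1:1 entry. It ranges from nil to 57 points with entry order when HR-MDS is at 10% (92.5% and 35%, against 92%).

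These sizes rest on assumed rates, a full 20:20 cohort and the order of entry. The calculation behind step 2 does not. The documents do not show that HR-MDS is less toxic, that the new doses carry the earlier sepsis rate, or that the SRC would be unaware of the cases. This is an inexpensive improvement worth making; it does not invalidate the pooled rule.

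**What to change.** Keep the pooled rule, and make these changes:

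- **Section 9.9.3.** State that, from the 8th R/R AML subject at a dose level, the same posterior (Beta(0.5, 0.5), 25%, 70%) is also computed for R/R AML alone and reported to the SRC as a non-binding prompt for review. Report the same for R/R HR-MDS once 8 are treated, because the dilution is symmetric. On the present boundaries, a 20-subject disease group uses 3 at 8, 4 at 10, 5 at 13 and 6 at 17.
- **Table 39.** Add unequal disease rates and the combined pooled-plus-disease rule. AML-only rows would duplicate what is there: the n = 21 row (84.2% at 35%, 92.3% at 40%) already equals the AML-only result at 20, since a cohort still open at 20 has at most 5 events and cannot reach 7 at 21.
- **Pooling wording.** Reconcile the permissive text in the Protocol Summary with the definite text in Sections 1.3.4 and 3.1.

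The change needs no new data and no more subjects, only one or two further calculations per SRC review. The price is the extra non-binding reviews in step 7: with the AML check alone, 4 points at a true 10%, 8.5 at 15% and 11 at 20%; with both checks, about 8, 17 and 21 to 22 points. The SRC should see these figures before adopting the checks.

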cohorts receiving CC-90009 at 3.6 mg Days 1-5 for enrollment, and new Part B cohorts will be enrolled under an alternative dosing regimen of 2.4 mg Days 1-7 and 3.0 mg Days 1-7, both to be evaluated in R/R AML and R/R HR-MDS. The selection of the alternative dose and schedule is based primarily on PK and PD analysis and safety and tolerability data. The new Part B cohorts will enroll subjects in parallel. Up to 6 subjects per cohort will be initially enrolled as a safety runin. The SRC will assess tolerability of the dose and schedule for these initial subjects that completed at least one cycle of study treatment based on the Part A stopping criteria (Section 7.2.8) and recommend further expansion of one or more cohorts. The expanded cohort(s) will be monitored for the excess toxicities including sepsis utilizing the non-binding Bayesian stopping criterion on a continuous basis (Section 9.9.3). Subjects of R/R AML and R/R HR-MDS enrolled in the expansion cohorts may be pooled for analysis of safety, PK, and PD. The SRC will continue to review safety and preliminary efficacy data regularly throughout the study and make recommendations about study continuation and dose modification, as appropriate.

Study Population

Men and women, 18 years or older, with relapsed or refractory AML or relapsed or refractory higher-risk MDS as defined by World Health Organization (WHO) criteria who are not suitable for other established therapies, will be enrolled in the study.

In Part A, only R/R AML subjects will be enrolled. In Part B, one of the initial cohorts will include R/R AML subjects, including subjects who relapse after allogeneic HSCT, who are in second or later relapse, who are refractory to initial induction or re-induction treatment, who are refractory to or relapsed after receiving hypomethylating agents (HMA failure defined as primary progression or lack of clinical benefit after a minimum of 6 cycles or unable to tolerate HMA due to toxicity), or who relapse within 1 year of initial treatment (excluding those with favorable-risk status; see Appendix H).

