Although CC-90009 modulates cereblon, the same molecular target of the IMiDTM immunomodulatory drugs (thalidomide and its analogues, eg, lenalidomide, pomalidomide), CC-90009 is mechanistically different. Interaction of CC-90009 with cereblon does not lead to degradation of the same set of proteins as the IMiDTM immunomodulatory drugs. Reproductive studies have not been conducted with CC-90009. Subjects will be required to follow the CC-90009 Pregnancy Prevention Plan (PPP) for Celgene Clinical Trials as described in Section 6.1.1 and Appendix L.

Subjects given CC-90009 at daily doses \geq 3.6 mg will be administered concurrent dexamethasone per Section 7.2. Subjects enrolled on other dose levels may be administered corticosteroid premedication as per SRC recommendation (eg, at the 3.0 mg dose level on the Days 1-7 and Days 1-10 schedules).

Subjects may be at risk for hypotension, infections (eg, sepsis), and other potential hematological and non-hematological toxicities. Subjects will be closely monitored for possible toxicity throughout the study by physical exam, vital sign and AE collection, through standard and specialized laboratory tests including hematology and serum chemistry labs and electrocardiogram (ECG). Refer to Section 7.2.13.4 for guidelines on infection prophylaxis, Section 7.2.13.8 for

guidelines on management and grading of hypotension, and Table 4 through Table 7 (D1-5 schedule), Table 31 through Table 38 (D1-3/8-10, D1-7, and D1-10 schedules).

Exploratory analyses of CC-90009 plasma exposures indicated a potential drug-drug interaction of CC-90009 with strong inhibitors of CYP3A4. Please refer to Section 7.2.15 for guidelines on dose modifications of CC-90009 for concomitant use of strong CYP3A4 inhibitors.

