After an initial 8 R/R AML subjects enrolled in Part B at dose level 3.6 mg Days 1-5 with dexamethasone premedication, a high rate of sepsis (75%) was observed in this cohort, and enrollment to both R/R AML and R/R HR-MDS cohorts were paused. There were no significant findings on demographic and baseline characteristics of R/R AML subjects enrolled at the same dose level (CC-90009 3.6 mg D1-5 with or without dexamethasone premedication) in Part A Dose Escalation (n = 11) and Part B Dose Expansion (n = 8). In both Parts A and B, preliminary analyses of pharmacokinetic data demonstrated increased CC-90009 exposure (1.56-fold) among subjects who developed sepsis as well as increased exposure (1.8-fold) among subjects who received concomitant strong CYP3A4 inhibitors. Preliminary modeling of exposure-sepsis and exposureclinical response relationships indicated that cumulative exposure of CC-90009 (AUC_{CUM}) was less predictive of sepsis than daily exposure (odds ratio [95% confidence interval]: 2.55 [1.17-6.65] for AUC_{CUM} as the predictor vs. 3.84 [1.35–13.35] for AUC₂₄ as the predictor) and that AUC_{CUM} was more predictive of clinical response than AUC₂₄ (odds ratio [95% Confidence Interval]: 5.06 [1.61–21.16] for AUC_{CUM} vs. 3.04 [0.97–13.07] for AUC₂₄). Comprehensive analysis of available PK, PD, efficacy, safety, and tolerability data led to the development of a strategy to reduce the risk of sepsis. The strategy includes evaluating doses of CC-90009 lower than 3.6 mg and schedules longer than 5 days that had been selected as the dose level for the Part B Dose Expansion. New cohorts in Part B will be enrolled at CC-90009 dose levels of 2.4 mg Days 1-7 and 3.0 mg Days 1-7. R/R AML and R/R HR-MDS subjects will be pooled in each cohort with 6 to 40 subjects enrolled in each cohort, including up to 20 subjects with R/R AML and up to 20 subjects with R/R HR-MDS in each cohort. The strategy also includes dose reduction of CC-90009 for subjects receiving concomitant strong CYP3A4 inhibitors. The new Part B cohorts will enroll subjects in parallel. Up to 6 subjects per cohort will be initially enrolled as a safety run-in. The SRC will assess tolerability of the dose and schedule for these initial subjects that completed at least one cycle of study treatment based on the Part A stopping criteria (Section 7.2.8) and recommend further expansion of one or more cohorts. The expanded cohort(s) will be monitored for the excess toxicities including sepsis utilizing the non-binding Bayesian stopping criterion on a continuous basis (Section 9.9.3). Subjects of R/R AML and R/R HR-MDS enrolled in the expansion cohorts will be pooled for analysis of safety, PK, and PD. The SRC will continue to review safety and preliminary efficacy data regularly throughout the study and make recommendations about study continuation, cohort continuation, and dose modification, as appropriate.

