7.2.6 Definition of Dose-Limiting Toxicity

During dose escalation, the DLT assessment period is Cycle 1 (at least 28 days and up to 42 days).

National Cancer Institute (NCI) Common Terminology Criteria for Adverse Events (CTCAE), Version 4.03 are used as a guide for the grading of severity of adverse events.

A DLT is defined as any of the following toxicities occurring within the DLT assessment unless the event can clearly be determined to be unrelated to CC-90009. Dose-limiting toxicities are described below:

- Any non-hematologic toxicity Grade \geq 3 EXCEPT for:
 - Grade \geq 3 nausea, vomiting, dehydration, or diarrhea that responds to standard of care.
 - Grade \geq 3 fatigue which resolves to Grade \leq 2 within 7 days (with optimal medical management).
 - Grade \geq 3 infection.
 - Grade 3 TLS, if controlled by medical management.
 - Grade 3 electrolyte abnormalities other than hypocalcemia (see below) correctable with supportive therapy.
 - Grade 3 laboratory evidence of hypocalcemia of < 24 hours duration in the absence of Grade \geq 3 clinical symptoms of hypocalcemia.
 - Grade \geq 3 AST or ALT elevation lasting \leq 7 days.
 - NOTE: any Grade \geq 3 AST or ALT in the setting of bilirubin elevation > 2xULN (> 2x baseline for subjects with Gilbert's syndrome) will be a DLT.
- Hematological toxicities as follows:
 - Prolonged myelosuppression, ie, marrow cellularity < 5% or persistent Grade ≥ 3 neutropenia at Cycle 1 Day 42 in the absence of leukemia.
- Any AE, unless clearly determined to be unrelated to the drug, and necessitating dose-level reduction during Cycle 1.

Isolated laboratory changes without associated clinical signs or symptoms (eg, hypomagnesemia, hypermagnesemia, hypophosphatemia, and lymphocyte count increased or decreased) may not be included in this definition. These findings will be discussed and reviewed by the SRC.

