7.2.8 Definition of Stopping Criteria

During Part A, dose escalation stops when ≥ 2 of up to 6 evaluable subjects in any dose cohort experience DLT during the DLT window.

During Part B, non-binding Bayesian stopping rules will be used to continuously monitor for excess toxicity defined as the occurrence of AEs during any cycle that would fulfill the DLT criteria specified in Part A or AEs leading to dose reduction or treatment discontinuation or AEs of sepsis. Details regarding the stopping rules are described in Section 9.9.3.

The SRC will convene regularly to review all the available safety, PK, PD, and efficacy data as well as the results of the Bayesian analysis of excess toxicity and in the event of the following:

- Bayesian stopping criteria are met.
- Unanticipated SAEs that are related to study treatment are reported.
- Death attributable to study treatment is reported.
- The sponsor or IRB/EC decides that subject safety may be compromised by continuing the study.

Decisions to stop the enrollment or terminate the study will be communicated promptly to investigators, to the Institutional Review Boards (IRBs)/Ethics Committees (ECs), Institutional Biosafety Committees ([IBCs], if applicable), and to the appropriate regulatory authorities.

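### The only count stated for the Part B safety run-in is the Part A DLT rule, under which sepsis does not count as such

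*Combined protocol and SAP*

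**What the plan says.** **Run-in.** Section 1.3.4 states: "Up to 6 subjects per cohort will be initially enrolled as a safety run-in". Section 3.1 has the SRC judge tolerability for "these initial subjects that completed at least one cycle of study treatment based on the Part A stopping criteria (Section 7.2.8"). The Protocol Summary and Section 1.3.4 use the same criterion, "based on the Part A stopping criteria (Section 7.2.8) and recommend further expansion of one or more cohorts".

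**The rule referred to.** In Section 7.2.8, Part A "dose escalation stops when ≥ 2 of up to 6 evaluable subjects in any dose cohort experience DLT during the DLT window".

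**What a DLT is.** Section 7.2.6 counts non-hematologic toxicity of Grade 3 or higher, with a list of exceptions. One is "Grade \geq 3 infection", with no upper grade and no exception for sepsis. Section 1.2.4 places sepsis among infections: "Subjects may be at risk for hypotension, infections (eg, sepsis), and other potential hematological and non-hematological toxicities".

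**Where sepsis is counted.** Sections 7.2.8 and 9.9.3 define a Part B excess-toxicity event that lists sepsis separately from DLT-type events. Section 3.1 applies the Bayesian rule built on it to the expanded cohorts. Section 9.9.3 starts the calculation once at least 8 subjects have had a cycle, and Table 15 starts at 8. For detail, Section 7.2.8 points onward: "Details regarding the stopping rules are described in Section 9.9.3".

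**Other safeguards.** The SRC reviews safety data regularly. Section 7.2.8 also convenes it on unanticipated related SAEs and when "Death attributable to study treatment is reported".

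**The concern.** Sections 1.2.3.1 and 1.3.4 present the Days 1-7 cohorts at 2.4 mg and 3.0 mg as part of a strategy to lower sepsis risk, after 6 of the first 8 Part B AML subjects on 3.6 mg Days 1-5 developed it. The run-in is the gate to expanding those cohorts. Its one numerical criterion leaves out the event that the strategy targets, although the plan has already defined an event that includes it. The SRC could act on sepsis, but it would have no stated number to set its findings against, and the written rule could be met while several of six subjects had sepsis.

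The text is also unsettled on three related points:
- Section 3.1 speaks of subjects who have completed a cycle, while Section 7.2.3 counts a DLT after any part of a dose. A subject who leaves during Cycle 1 may or may not count.
- Section 7.2.8 drops the treatment-related qualifier that Section 9.9.3 puts on events leading to dose reduction or discontinuation.
- Section 9.9.3 says that the analysis is run whenever a qualifying event occurs, but also sets a minimum of 8 subjects.

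**Working it through.** **1. The plan's own figures.** With the Beta(0.5, 0.5) prior of Section 9.9.3, the pause boundary is the smallest x with 1 − F(0.25; 0.5 + x, 0.5 + n − x) > 0.70, where F is the Beta distribution function. This reproduces all ten entries of Table 15, from 3 of 8 to 12 of 39. An exact recursion with a look after every subject from n = 8 reproduces Table 39 within 0.1 point:

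| True event rate | 10% | 15% | 25% |
|---|---|---|---|
| Pause at n = 8, recomputed | 3.8% | 10.5% | 32.1% |
| Pause at n = 8, Table 39 | 3.8% | 10.5% | 32.2% |
| Pause by n = 39, recomputed and Table 39 | 6.5% | 19.6% | 62.9% |
| Pause by n = 8 if looks began at n = 1 | 23.5% | 36.3% | 60.0% |

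The last row is far from Table 39, so the table assumes no look before 8. This supports the minimum of 8 as the working rule.

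**2. Chance that the run-in rule is met.** Let s be the sepsis rate, o the rate of DLT from other causes, and f the share of septic subjects who also score a DLT by another route. Then p = 1 − (1 − o)(1 − s·f), and P(met) = (1 − p)^6 + 6p(1 − p)^5. The documents give neither o nor f, so both are assumptions, as is independence.

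- f = 0, o = 0.10: 0.531 + 0.354 = 0.886 for any s. With o = 0.05 it is 0.967, and with o = 0.15 it is 0.776.
- s = 0.75, o = 0.10: f = 0.10, 0.25, 0.50 gives p = 0.168, 0.269, 0.438 and P(met) = 0.735, 0.490, 0.179.

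**3. The next look, at 8 subjects.** The sepsis rates come from Section 1.2.3.1: 75% on the closed regimen, 29% at 3.0 mg (n = 24) and 15% at 2.4 mg and below (n = 13), the last two from Part A. They are not restricted to Cycle 1. Take f = 0 and o = 0.10, and condition on 0 or 1 DLT in the first six. The other run-in subjects are septic with probability s; each of the last two has an event with probability 1 − 0.90(1 − s).

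| Sepsis rate | 75% | 29% | 15% |
|---|---|---|---|
| P(≥3 of 8), sepsis alone | 99.6% | 42% | 11% |
| P(≥3 of 8), sepsis or other DLT, run-in passed | 99.7% | 56% | 23% |

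**4. The attributable-death route.** Section 1.2.3.1 lists eight subjects with a related fatal event. Sepsis terms account for 3 + 1 + 1 + 1 + 1 = 7, against 24 subjects with sepsis. One such death is enough to convene the SRC, so the unit is the run-in. Applying 7/24 per septic subject, 1 − (1 − 7s/24)^6 = 77%, 41% and 24% at s = 75%, 29% and 15%.

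**5. Illustration of a run-in count.** The plan's own posterior at 2 of 6 is 0.702; at 1 of 6 it is 0.348. Under Beta(0.25, 0.75), also centred on 25%, 2 of 6 gives 0.622 and does not cross 0.70. Adding a 2-of-6 look on the Section 9.9.3 event gives, per cohort:

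| True event rate | 10% | 15% | 25% |
|---|---|---|---|
| Run-ins flagged | 11% | 22% | 47% |
| Cumulative pauses by n = 40, current plan | 6.5% | 19.6% | 63.1% |
| Cumulative pauses by n = 40, with the added look | 13.3% | 28.8% | 69.0% |

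**The case against.** The strongest reply is that the SRC already reviews every run-in, meets regularly (monthly is the example given), looks at each subject with a qualifying event including sepsis, and closed the 3.6 mg cohorts over sepsis before the Bayesian rule existed. This stands. A reader might infer that sepsis in the first six subjects would go unexamined; the documents do not support that. What is missing is a written reference count. The death trigger is also a real safeguard when counted per run-in, though a partial one.

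Nor is sepsis shut out of the DLT count. A Cycle 1 dose-level reduction, or a non-exempt event such as hypotension needing vasopressors, would count. The 0.89 is therefore a bound at f = 0.

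The 75% rate belongs to a closed regimen. The new cohorts use lower daily doses, require dose reduction with strong CYP3A4 inhibitors and pool HR-MDS subjects. The 29% and 15% rates are nearer, and even they come from small Part A groups.

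It is tempting to say that the DLT rule missed a sepsis signal when 3.6 mg Days 1-5 with dexamethasone was declared an MTD. Sepsis at that dose and schedule in Part A was 2 of 11, so the documents do not show this.

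Finally, 2 of 6 should not be read as the right composite cut-off. It clears the threshold by 0.002 under a prior that is only optional. With 15% sepsis and 10% other DLT the composite rate is 1 − 0.90 × 0.85 = 23.5%, below the plan's 25% limit, yet 43% of run-ins would be flagged.

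**Conclusion.** The point holds as a gap between the run-in rule and the plan's own excess-toxicity event. No stated count at the run-in includes sepsis as such, and the first count that does comes at 8 subjects. The gap is short. At 75% sepsis the 8-subject look closes it almost at once. At 29% it triggers after a passed run-in only about 56% of the time, assuming 10% other-cause DLT, f = 0, independence and Part A sepsis rates applied in full.

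This is an inexpensive improvement in clarity and safety monitoring. It does not show that the SRC would overlook sepsis, and it does not establish a particular stopping count. The evaluability, treatment-related and minimum-of-8 wordings are ambiguities to settle in the same edit.

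**What to change.** Reconcile the Protocol Summary (Part B) and Sections 1.3.4, 3.1, 7.2.3, 7.2.6, 7.2.8 and 9.9.3:

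- State that the run-in assessment uses the Section 9.9.3 excess-toxicity event, including sepsis, as a non-binding reference for the SRC.
- State that subjects who have an event or leave during Cycle 1 are counted.
- Word the event identically in Sections 7.2.8 and 9.9.3.
- Say whether the analysis run at each qualifying event applies below 8 subjects.
- Have the sponsor choose the run-in count and report its operating characteristics beside Table 39, with their sensitivity to the prior.

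The cost is protocol wording and one added set of operating characteristics, with no extra subjects or procedures. The downside is more pauses at acceptable event rates, by an amount that depends on the count chosen. In the 2-of-6 illustration, cumulative pauses at a true 10% rate about double, from 6.5% to 13.3%.
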